5.1 Locating Participants

Retention in DISC was excellent; 89.4% of girls completed last visits, which were conducted on average 7 years after randomization. Extraordinary efforts will be undertaken to see all participants.

Because the participants were minors when they were active in DISC, informed consent was provided by the parents/guardians, and new HIPAA regulations may require that we initially contact participants through their parents/guardians or some intermediary (e.g. physician, school). Each center will follow the guidance provided by their IRB for contacting participants. In general, a letter will be sent to the participants' parents last known address informing them about the plans for a follow-up DISC visit, what would be involved, and asking them to have their daughter contact us. The envelope will be marked 'Forwarding Address Requested', so that the post office will provide us new addresses for individuals who have moved. A telephone call will be made to the last known telephone number within 2 weeks of mailing the letter. Whenever possible, a DISC staff member who knew the family will make the call. Because DISC was a family intervention and parents know the DISC staff, we are confident that parents will assist us in contacting their daughters.

Participants not found using the above procedure will be traced using several sources: 1) the two friends/relatives identified during the DISC trial as individuals who did not live in the household but would know where to locate the family will be contacted; 2) parents will be contacted at their place of

employment; 3) post offices will be asked to provide forwarding addresses; 4) participants' personal physicians will be contacted; 5) local telephone books will be searched; 6) internet based telephone, residential address and email address websites will be searched. Additionally, in some cases, reverse (criss-cross) directories may be used to obtain telephone numbers of neighbors to contact. The only information that will be disclosed to neighbors in this case is the participant's name, that she was a prior neighbor, and that we are trying to locate her because she previously participated in a research study of diet in healthy people and we would like to invite her to participate in another research study.

For participants who cannot be found locally, identifiers including names, last known address and telephone number, and contact information will be forwarded to a commercial search firm.

5.2 Scheduling Clinic Visits

All clinic visits will take place during the luteal phase of participants' menstrual cycles. Although follicular phase estradiol levels in the intervention group were significantly 28% lower than the usual care group at Year-5 visits, we did not observe any significant differences in estrogens or androgens in the follicular phase of the menstrual cycle at last visits. However, at their last DISC visits, the intervention group had significantly 53% lower serum progesterone levels during the luteal phase of their menstrual cycles compared to the usual care group. To maximize power to observe differences in progesterone and possibly estrogens at the proposed follow-up visit, all visits will be scheduled to take place during the luteal phase of the menstrual cycle.

Because time from ovulation to onset of next menses is more constant than time from previous menses to ovulation, we will time visits in relation to expected date of start of next menses. The participant in consultation with clinic staff will select a target date for the clinic visit based on when she usually gets her period. When the participant starts her last period expected before the target date, she will call the clinic. Clinic personnel will record the date the participant started her last period and then schedule the visit to occur 3-4 days (± 2 day window) before her anticipated start of next menses based on date of start of last period and usual cycle length. We also considered timing the clinic visit in relationship to ovulation by asking participants to use urine ovulation kits. However, participants would have to come to the clinic in about a week after ovulating, which would give them little time for planning to take time off from school or work and in some cases fly to the clinical center. Additionally, using this approach we would include only ovulatory cycles, which would remove a source of variation in the hormone data.

6.0 STUDY DESIGN

A follow up study of women who participated in DISC during adolescence will be conducted.

- Number of groups: 2
- The sequencing of treatment: None
- Method of subject allocation: Random
- Type of control: Usual care
- Blinding procedure: All data collection personnel will be blinded to treatment group.
- The essential characteristics of the subject population: Females currently in their 20s who previously participated in the DISC study as adolescents
- The duration of exposure to individual subjects: Average 7 years in DISC trial. No additional interventions in current study.
- The total expected duration of the study: 4 years.
- The drug dosage/device usage schedule: The DISC diet was a balanced food pattern that achieved the following goals: limit intake of total fat to <28% calories, with <8% of calories from saturated fat, <9% of calories from polyunsaturated fat and the remainder from monounsaturated fat, limit cholesterol intake to 75mg/1000 calories not to exceed 150 mg/day, maintain protein intake at 14% calories (2/3 animal protein, 1/3 vegetable protein), and maintain carbohydrate intake at 58% calories.

7.0 MEASUREMENT OF EFFECT

Intervention and usual care group participants' serum progesterone and estradiol, bone mineral density and breast density will be compared as described under statistical considerations. Data on these endpoints and potentially confounding variables will be collected at a clinic visit. This section provides an overview of the clinic visit and a description of data collection procedures.

7.1 Clinic Visit

All data collection for an individual participant will be conducted on a single day. It is anticipated that the visit will take several hours to complete. Participants will be asked to fast for 12 hours before coming to the clinic. After a urine pregnancy test and venipuncture, the participant will be weighed and her height will be measured. She will be fed a standard meal, complete questionnaires, bone density will be measured by DEXA, breast density will be measured by MRI, and an in-person 24-hour dietary recall will be conducted. Two additional 24-hour dietary recalls will be conducted by telephone in the following 2 weeks. Trained and certified individuals who are masked to treatment assignment will perform all data collection.

We will pay transportation costs for participants who live out of town. For participants who have to fly, one night lodging will be provided. Participants who have moved and live closer to a different DISC clinical center will have the option of going to that center for evaluation. Participants who attend the clinic visit be reimbursed \$500 for participating in this very involved study.

7.2 Anthropometry

Height will be measured by a stadiometer and weight will be measured by an electronic scale. Participants will be clothed in a hospital gown without shoes. Consistent with earlier DISC measurement acceptability criteria, if height measurements do not agree within .5 cm or if weight measurements do not agree within .2 kg, measurements will be performed a third time and the two closest values will be averaged.

7.3 Dietary Assessment

Three 24-hour dietary recalls will be collected within 2 weeks of the clinic visit by Nutrition Coordinating Center certified nutritionists using Nutrition Data System for Research (NDS-R). This is a Window's based direct data entry system that prompts the nutritionist performing the interview to ask appropriate questions regarding foods. For example, the nutritionist is prompted to ask the participant about the percent fat in milk consumed and serving size. This state of the art system calculates nutrient composition and is used extensively in nutrition research. The system also has the capability to calculate servings of subcategories of fruits, vegetables and sweetened beverages. Efforts to complete other categories are underway and are expected to be ready for use in the DISC follow-up analyses. Two recalls will be conducted on weekdays and one will be conducted on a weekend day. The first recall will be a face-to-face recall with the nutritionist. The second and third recalls will be by telephone. Two dimensional food models will be used to help participants estimate serving sizes. These procedures are the same as were used previously in DISC and participants will be familiar with the approach. A 20% sample of recalls will be randomly selected for evaluation at the Nutrition Coordinating Center for quality assurance.

7.4 Physical Activity

Physical activity will be measured using the Modifiable Activity Questionnaire developed by Dr. A. Kriska [126]. The questionnaire captures leisure time and occupational/school physical activity, is age appropriate and has excellent test-retest reliability (r=.92 for individuals 21-36 years of age) [126]. It has been validated against Caltrac activity monitor (r=.6-.8) [126] and doubly labeled water (r=.7)

[127]. A copy is included in Attachment B. We also will repeat the questions about usual physical activity used in the original DISC study for comparison (Attachment B).

7.5 Menses Dates

Participants will report date of last menses and record date of start of next menses after the clinic visit on a postcard and return it to the clinic. Because data on start of next menses will be important for interpreting serum hormone and breast MRI data, if a postcard is not received within 5 days of estimated start of next menses, clinic staff will call the participant to see if she started her period. If she has, the date will be recorded. If she has not, clinic staff will call her each week until she has her period.

7.6 Psychosocial Assessments

Because affective disorders can lead to alterations in HPO axis functioning [128-130], we will collect limited data on these characteristics to evaluate for potential confounding. Depression will be measured using the Center for Epidemiological Studies-Depression scale (CES-D) [131]. To reduce participant burden, we will use the 11-item short form [132]. The short-form reproduces the same four factor structure as the original CES-D (i.e., depressed affect, positive affect, somatic complaints, and interpersonal problems), has high reliability, and is strongly correlated with the original full scale. General levels of anxiety will be measured using the 20-item trait anxiety scale of the Spielberger State-Trait Anxiety Inventory (STAI) [133], which has been shown to have high internal consistency and is well correlated with other dispositional measures of anxiety. The STAI has proven to be effective in screening college students for anxiety problems and has been widely used with a variety of populations (e.g., normal, healthy adults; medical patients).

7.7 DISC Medical History Questionnaire

A DISC Medical History questionnaire (Appendix B) will be used to collect updated information on demographic characteristics (education, occupation, marital status, income, ethnicity); medical history (serious or chronic illnesses, hospitalizations,); medications (current medications and detailed current and past use of hormonal contraceptives including brand names, age started and duration of use); menstrual history (age at menarche (a few participants had not reached menarche at last visits), cycle regularity and length); reproductive history (number and dates of pregnancies and births; number, dates and duration of lactation); dietary supplements (supplements with hormonal properties, vitamins and minerals including calcium); alcohol use (frequency and amount, binge drinking); tobacco use (current, past, cigarettes/day); family history of cancer (update information on cancer among first degree relatives).

7.8 Blood Sample Collection and Processing

A total of 55 ml of blood will be collected by venipuncture using standard procedures with the participant in the supine position. Three 15ml red top serum separator tubes for hormones and storage and one 10 ml yellow top ACD tube for DNA extraction will be collected from each participant. Serum and lymphocytes will be separated and aliquoted at the clinical centers and stored at -80°C until shipped to the Fox Chase Cancer Center (FCCC) Repository. Shipments to FCCC will be made monthly by overnight Fed-Ex with samples packaged in dry ice. Each participant's specimens will be divided in half and sent to FCCC in 2 separate shipments so that if there is an accidental thaw, only half of samples are affected. Serum for hormone assays will be stored at FCCC at -80°C until shipped to the Central Hormone Laboratory for analysis at the end of data collection. Additional serum will be stored for future assays. High molecular weight DNA will be extracted from lymphocytes using standard phenol/chloroform techniques and stored at 4°C for future use.

7.9 Serum Hormones

All hormone assays will be conducted under the direction of [name] at the Reproductive Endocrine Research Laboratory, Department of Obstetrics and Gynecology, University

of Southern California Keck School of Medicine. [name] has been supervisor and director of this laboratory since 1972. The laboratory has extensive experience in measuring steroid, peptide and protein hormones using well-validated methodology that has been published. All hormone assays will be performed at the end of data collection. Serum samples for hormone assays will be batched at FCCC; batches will be balanced on treatment group. Masked quality control samples indistinguishable from participant samples will be included in batches. Samples will be shipped to the laboratory on dry ice. The hormones will be analyzed by specific immunoassays as described below.

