7.9.1 Progesterone

Progesterone will be quantified by radioimmunoassay (RIA) following its extraction with ethyl acetate:hexane (2:3) and Celite column partition chromatography [136]. Approximately 1000 d.p.m. of ³H-progesterone will first be added to each serum sample to follow procedural loss. The RIA of purified progesterone will use iodinated progesterone in conjunction with a specific antiserum against progesterone. After an appropriate incubation period, a second antibody is used to separate antibody-bound progesterone from unbound progesterone. The resulting progesterone values will be corrected for procedural loss. Sensitivity of the assay is 0.2 ng/ml; intraassay and interassay coefficients of variation (CVs) are 8% and 9%, respectively.

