7.9.2 Estradiol

Estradiol will be measured by RIA following extraction and Celite column partition chromatography [137]. The extraction step will utilize ethyl acetate:hexane (2:3). Following evaporation of the organic solvents, the extract will be applied on a column of Celite impregnated with ethylene glycol. Estradiol will be separated by elution with 15% ethyl acetate in isooctane and 40% ethyl acetate in isooctane, respectively. After evaporating the eluates, the residues will be redissolved in assay buffer, and appropriate aliquots will be taken for RIA. Each RIA uses a highly specific antiserum in conjunction with an iodinated radioligand. Following an appropriate incubation period, antibody-bound and unbound estradiol is separated using a second antibody. The antibody-bound fraction is then counted after centrifugation. Sensitivity of the estradiol assay is 5 pg/ml; intraassay and interassay CVs are 9.3% and 11.4%, respectively.

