12.2 Data Analysis

All analyses will be performed using analysis files created by adding follow-up data to the main DISC database with verification by manual checking. SAS (SAS Inst., Cary, NC) will be the primary software used for analysis supplemented with S-Plus (Insightful Corp., Seattle, WA) and Stata (Stata Corp., College Station, TX).

Because DISC was a clinical trial, analysis of the specific aims will be performed by randomized treatment assignment. Mean serum progesterone will be compared between the intervention and usual care groups without regard to compliance with the intervention, attendance at intervention sessions, or attendance at earlier DISC clinic visits. Because hormonal contraceptives contain progesterone, only women not using hormonal contraceptives will be included in analysis of treatment group differences in serum progesterone levels. The distribution of serum progesterone values will be examined to determine whether transformation is appropriate prior to analysis. In previous DISC analyses, we In transformed hormone concentrations to improve normality and decrease dependence of the variance on concentration. We anticipate that In transformation of progesterone data collected at the proposed follow-up visit will also be appropriate, but a final decision will be made after examining the data. The analytical approach will depend on the distributions of age, race, and menstrual cycle day when blood was collected at the clinic visit in the two treatment groups. These characteristics are potential confounders that would not be affected by the intervention. If the treatment groups are balanced on these characteristics, means can be estimated directly and statistical significance of the treatment group differences can be tested using a Student's t-test. If the participants in the treatment groups are not balanced on these characteristics and there is evidence for confounding, we will estimate adjusted means and test for statistical significance using linear models. We used analysis of covariance to compare adjusted treatment group means in previous DISC hormone analyses.

The effect of missing progesterone data on observed treatment group differences will be evaluated using the multiple imputation method of Rubin [89], in which multiple datasets are constructed, analyzed, and results combined so that the underlying variability of the outcome is preserved.

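### Assay batches are balanced on treatment group but left out of the hormone comparison, so the test is slightly conservative: about 1 to 3 power points for estradiol, under 1 for progesterone

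*Protocol*

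**What the plan says.** Section 7.9 (Serum Hormones) has all assays run at the end of data collection and sets up the batches at the FCCC repository: "batches will be balanced on treatment group". Masked quality control samples are added to them.

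The assay precision is given for each hormone. For progesterone (7.9.1), "intraassay and interassay coefficients of variation (CVs) are 8% and 9%, respectively". For estradiol (7.9.2), "intraassay and interassay CVs are 9.3% and 11.4%, respectively".

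Section 12.2 (Data Analysis) fixes the comparison. "The analytical approach will depend on the distributions of age, race, and menstrual cycle day when blood was collected at the clinic visit". "If the treatment groups are balanced on these characteristics, means can be estimated directly", and the difference "can be tested using a Student's t-test". If the groups are not balanced on these three characteristics and there is evidence for confounding, adjusted means come from linear models. Estradiol, a secondary aim, follows the same approach. Batch appears nowhere in the analysis text, including the list of secondary covariates and effect modifiers.

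**The concern.** Balancing batches on treatment makes batch a blocking factor. The difference in group means is then free of batch effects, because each batch contributes equally to both groups. An unadjusted t-test does not know this. Its variance estimate pools all within-group variation, including the part between batches, so the standard error is larger than the true sampling error of the difference.

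The adjustment rule cannot repair this. A term enters only if it is one of three named characteristics, is unbalanced and confounds. A factor balanced by design fails the imbalance condition, so the rule keeps out a term whose use is to reduce error variance and not to remove bias.

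What is at stake is efficiency. The cohort is fixed at 301, and Table 1 expects only 48-68 women per group in the hormone analyses, so precision cannot be bought with more participants. Estradiol is more exposed than progesterone: its interassay CV is larger and its planning SD smaller.

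**Working it through.** **Inputs**
- SD of ln progesterone 0.52 (12.3.1) and of ln estradiol 0.32 (12.3.2), each from 9 usual care participants and adjusted for age and cycle day.
- Interassay/intraassay CVs: progesterone 9%/8%, estradiol 11.4%/9.3% (7.9.1, 7.9.2).
- Two-sided alpha 0.05 and 80% power (Table 1).

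**1. Reproduce Table 1.** Detectable ln difference = SD × √(2/n) × (1.960 + 0.842). For n = 60, 48, 68, 54:
- progesterone 0.266, 0.297, 0.250, 0.280;
- estradiol 0.164, 0.183, 0.154, 0.173.

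All agree with the table, so the baseline is sound.

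**2. Between-batch variance.** On the ln scale a CV is close to an SD. The protocol does not say whether the interassay CV includes intraassay error, so there are two bounds.
- Estradiol, upper (CV purely between batches): 0.114² = 0.0130; 0.0130/0.32² = 12.7%.
- Estradiol, lower (CV is total assay variation): 0.114² − 0.093² = 0.00435; 0.00435/0.32² = 4.2%.
- Progesterone, upper: 0.09²/0.52² = 0.0081/0.2704 = 3.0%.
- Progesterone, lower: (0.09² − 0.08²)/0.52² = 0.0017/0.2704 = 0.6%.

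**3. Within-batch SD**, if the planning SD includes between-batch variance: σw = √(SD² − between-batch variance).
- Estradiol: 0.313 (lower bound), 0.299 (upper bound).
- Progesterone: 0.518, 0.512.

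**4. Behaviour of the unadjusted t-test.** With balanced batches the difference varies with σw, while the test divides by the full SD. For many batches and large samples:
- type I error = 2 × [1 − Φ(1.960 × SD/σw)];
- detectable difference = √(2/n) × (1.960 × SD + 0.842 × σw);
- power at d = Φ([d/√(2/n) − 1.960 × SD]/σw).

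With batch in the model, SD is replaced by σw throughout. At n = 60, √(2/n) = 0.1826, and d is the Table 1 value (0.164 for estradiol, 0.266 for progesterone):

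| | Type I error, t-test | Power, t-test → adjusted | Detectable ln difference, t-test → adjusted |
|---|---|---|---|
| Estradiol, lower | 0.045 | 80.7% → 81.8% | 0.163 → 0.160 |
| Estradiol, upper | 0.036 | 81.8% → 85.2% | 0.160 → 0.153 |
| Progesterone, lower | 0.049 | 80.1% → 80.3% | 0.266 → 0.265 |
| Progesterone, upper | 0.047 | 80.4% → 81.2% | 0.265 → 0.262 |

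As percentages (1 − e^−d), the estradiol detectable difference is 15.0% → 14.8% at the lower bound and 14.8% → 14.2% at the upper.

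**5. Simulation check** (60 per group, 3 or 6 balanced batches, 20,000 runs). For estradiol the t-test had a type I error of 0.038-0.048, against 0.048-0.052 adjusted, and lost 0.8-3.2 power points. For progesterone it lost at most about 0.6 points. With few batches the conservatism is a little weaker than the formula gives.

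**6. If the planning SDs contain no between-batch variance**, for instance because the 9 samples shared one run, the total estradiol SD becomes √(0.32² + 0.00435) = 0.327 to √(0.32² + 0.0130) = 0.340, and σw is 0.32. The same formulas at d = 0.164 give 79.0% to 76.6% power unadjusted and about 80% adjusted. The loss is again about 1 to 3.5 points, but adjustment then restores the Table 1 figure and does not improve on it.

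**The case against.** The strongest reply is that nothing here is invalid. Balancing protects the treatment contrast whether or not batch is modelled, the estimate is unbiased, and the test errs on the safe side. Nuisance terms are often left to an analysis plan, and the wording of 12.2 leaves some room for judgement. This stands as far as validity goes. It does not fully answer the point, because 12.2 names the test, the candidate covariates and the condition for using them, and a balanced batch cannot meet that condition.

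The second reply is that the estradiol figures are fragile, and much of it stands:
- The interassay CV is not defined, which alone moves the share between 4.2% and 12.7%.
- An SD of 0.32 from 9 women has a 95% interval of about 0.22-0.61 (8 df), so the share could lie anywhere from about 1% to 28%.
- That SD is already adjusted for age and cycle day. An unadjusted t-test would have a larger SD if either predicts estradiol, and batch would be a smaller share.
- Batches are formed at the repository, and the protocol does not say that one batch is one assay run. If a batch is split across runs, a batch term removes less.

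A reader might infer a larger gain: that adjustment cuts the estradiol standard error by 2-7% and moves the detectable difference down from the 15.1% in Table 1. That counts the benefit of balancing twice. The balanced design already lowers the true sampling error of the difference, so the unadjusted test can detect about 14.8-15.0%, and only the remaining step to 14.2-14.8% comes from the model. A reader might also infer bias, or a real loss for the primary aim; the protocol's figures support neither.

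**Conclusion.** The point holds as a minor efficiency matter. The protocol builds a block into the assay design and specifies an analysis that ignores it, which makes the hormone tests slightly conservative. The cost is about 1-3 power points for estradiol and under 1 point for progesterone, so the primary comparison is essentially unaffected.

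The direction follows from the balanced design wherever batches differ. The size depends on four things that the protocol does not settle: what the interassay CV contains, how well 9 women estimate the SDs, whether those SDs include between-batch variance, and whether a batch corresponds to an assay run. The uncertainty in the SDs is larger than the effect itself.

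**What to change.** In 12.2, state that ln progesterone and ln estradiol will be compared between groups with a linear model that includes assay batch as a fixed or random block, whatever the balance on age, race and cycle day. Define batch as the assay run, or include the run if a repository batch is split, and keep the batch/run identifier in the analysis file; the protocol does not say that it will be kept.

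The cost is one model term, one identifier and, for a fixed block, one degree of freedom fewer than the number of batches, against 96-136 women in total (2 × 48 to 2 × 68). The number of batches is not given but should be small by comparison. Nothing changes in sample handling or conduct. The gain for progesterone is slight; using the same model for both hormones mainly keeps the two analyses consistent with the assay design.
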